### *14.2.3 Measurement on prostaglandin E2 and arachidonic acid pathway related metabolites associated with sulindac activity*

The NSAIDs are highly efficacious for the management of musculoskeletal pain associated with prostaglandin (PG)-mediated inflammation. NSAIDs act by blocking cyclooxygenase (COX)-1 and -2

enzymes metabolism of arachidonic acid (AA) to the PGs. In addition to the well-known COX-mediated metabolism, AA and other unsaturated fatty acids ( $\Omega$ -6 and  $\Omega$ -3) are also metabolized by two other enzyme families: the lipoxygenases (LOX) and members of the cytochrome P450 (CYP450) enzyme family. Collectively, these  $\Omega$ -6 and  $\Omega$ -3 can be metabolized to over 100 metabolites known as 'oxylipins' (see Figure 3). Oxylipins exhibit a wide spectrum of biological activity including pro- and anti-inflammatory effects as well as anti-tumor activity and acting as inducers and inhibitors of pain depending on the enzymes activated and availability of substrate.

#### 14.2.3.1 *Reverse phase chromatography with UPLC-MS for oxylipin profiling*

Metabolite profiling will be performed using a QToF mass spectrometer to give highly accurate (<5 ppm), reproducible mass measurements. We will also collect  $MS^E$  data at both low (5V) and high (50V) collision energies in order to obtain fragmentation data simultaneously (Plumb et al. 2006). Samples will be analyzed in positive and negative electrospray modes. Leucine enkephalin will be infused into the instrument to provide a lock mass, and the system will be calibrated using HCOONa. Data will be collected in centroid mode with a scan range of 50–1000 m/z, with lockmass scans averaged over 3 scans to perform mass correction.

**Figure 3: Oxylipin metabolites of the  $\Omega$ -6 fatty acid, arachidonic acid (AA).** Sulindac targets cyclooxygenase (COX) pathways and reduce production of inflammatory prostaglandins (PGs; down red arrow). Off-target effects include inhibition of 5-Lipoxygenase (LOX), resulting in reduced 5-hydroxyeicosatetraenoic acid (HETE), and upregulation of cytochrome P450 enzymes, CYP1A and 1B (resulting in increased Epoxyeicosatrienoic acids; EETs). The hypothesis is that inhibition of one enzyme should result in compensatory up-regulation of alternate pathways in order to metabolize AA, resulting in an increase in analgesic EETs; up red arrow. Biological functions are noted below those oxylipins that are the focus of the specific aims. sEH: soluble epoxide hydrolase; LT: leukotriene; HETE: hydroxyeicosatetraenoic acid; Lx: lipoxin; DiHETrE: dihydroxyeicosatrienoic acid.

#### 14.2.3.2 Mass spectrometry (MS) data preprocessing

MS profiles will be pre-processed using Waters' TransOmics software, which has been developed specifically for Waters instrumentation and metabolomics studies. TransOmics algorithms are set to use only "well behaved" peak groups for alignment of datasets and then fill missing peaks using baseline raw data, allowing for subsequent data analysis.

#### 14.2.3.3 Lipidomics approach and metabolite identification

Metabolite identification of 108 oxylipins relies heavily on the use of standards. However, a major goal of the training for this work is to expand the methodology to captures numerous metabolites. Therefore, where the structural identity (i.e. common name) of metabolites associated with pain and/or sulindac intervention is unknown, they will be identified using TransOmics, The Human Metabolome Database (hmdb), METLIN ([metlin.scripps.edu](http://metlin.scripps.edu)), Platform for RIKEN Metabolomics, Chemspider, Lipidmap, Lipidbank, National Institute of Standards and Technology (NIST) chemical web book, and in-house databases.(Wishart et al. 2009; Cui et al. 2008; Smith et al. 2005; Kopka et al. 2005; Akiyama et al. 2008) Where necessary, specimens will be pooled and reconstituted at higher concentrations to enable

effective structure elucidation. Tandem mass spectrometry (MS/MS) and MSE using UPLC-QToF-MS can generate detailed fragmentation patterns for unknown metabolites. The high mass accuracy (<2 ppm) facilitates generation of empirical formulae (parents and fragments), aiding structural characterization. Pure standards of identified metabolites not already contained in the internal standard mix will be purchased and spiked into samples to confirm identification.

#### 14.2.3.4 *Pathway integration*

Relevance of identified metabolites to BC and pain-related pathways will be determined using literature review and pathway integration databases [e.g. ConsensusPathDB ([cpdb.molgen.mpg.de/](http://cpdb.molgen.mpg.de/)), Kryo Encyclopedia of Genes and Genomes (KEGG; [www.genome.jp/kegg/kegg3a.html](http://www.genome.jp/kegg/kegg3a.html)), MetaCyc, (Caspi et al. 2012) and LIPID MAPS. This work is a particular area under rapid applications expansion for which onsite training and workshop activities will be of high value, allowing me to analyze my own data and become expert in the field.

### 14.3 Risk associated with Blood and Urine Sample Collection

There is minimal to no risk associated with urine collection to the participants with minor risk of bruising or soreness at the site of blood draw.

## 15 PARTICIPANT ELIGIBILITY

### 15.1 Eligibility criteria:

- a. Postmenopausal women with of first incidence of early stage (stages 0 – III) hormone receptor positive breast cancer stabilized on aromatase inhibitor (AI) therapy for at least 3 months
- b. Patients must have started on AI at least three months before consenting with plans to continue on AI therapy for a minimum of 16 months (12 months for AI only arm) or until the end of the study intervention.
- c. Patients must have an unaffected, non-irradiated contralateral breast with a baseline BD score of  $\geq 25\%$  as measured by standard digital mammography (BIRADS score  $\geq 2$  or scattered fibroglandular densities at least heterogenous or greater) performed within 12 months of consent to the study
- d. A willingness to follow the study protocol, as indicated by provision of informed consent to participate
- e. A willingness to avoid taking NSAIDs outside of the trial (rare NSAID use for musculoskeletal symptoms accepted, and/or daily use of aspirin < 81 mg is allowed for the duration of the study) [apply only to AI Sulindac arm]

- f. Normal renal function as determined by a serum creatinine  $\leq$  upper limit of normal (ULN= 1.5mg/dl) or a creatinine clearance above 60 ml/min [apply only to AI Sulindac arm]
- g. No known contraindication to NSAID use [apply only to AI Sulindac arm]
- h. Normotensive or controlled blood pressure (< 140/90) on no more than two anti-hypertensive medications [apply only to AI Sulindac arm]

## **15.2 Exclusionary criteria:**

- a. Current or anticipated need for daily aspirin or NSAID. Daily use of no more than 81 mg of aspirin for cardiovascular protection is permitted.
- b. Known intolerance to NSAIDs [applies only to AI + Sulindac arm]
- c. Age  $\geq$  75 years
- d. History of cardiovascular disease including prior myocardial infarction, angina, stroke, or transient ischemic attack (TIA) [applies only to AI + Sulindac arm]
- e. Diabetes requiring drug therapy [applies only to AI + Sulindac arm]
- f. Current smoker [applies only to AI + Sulindac arm]
- g. Current uncontrolled hypertension [applies only to AI + Sulindac arm]
- h. Blood pressure > 140/90 at baseline by home monitoring [applies only to AI + Sulindac arm]
- i. History of GI bleeding in the past 5 years. [applies only to AI + Sulindac arm]
- j. Patients with active GI symptoms including burning pain in the middle of the stomach between meals or at night, stomach bloating, heartburn, nausea or vomiting despite PPI therapy. [applies only to AI + Sulindac arm]
- k. History of a bleeding diathesis or current anticoagulant therapy [applies only to AI + Sulindac arm]
- l. History of claustrophobia
- m. Have electrically, magnetically, or mechanically activated implants including cardiac pacemaker, cochlear implants, magnetic surgical clips or prostheses.
- n. Current use of any corticosteroids or immune suppressive therapies [applies only to AI + Sulindac arm]

## **16 STUDY PARTICIPANT IDENTIFICATION**

Participants who have been consented will be identified on study-related documentation and forms with a unique 7 alphanumeric study identifier. These numbers will be issued to participants sequentially

and no participant identification numbers will be re-assigned in the event that the participant is withdrawn from the study.

## **17 ASSIGNMENT TO STUDY GROUPS**

The study will be a non-randomized trial with participants explicitly consented to either AI Sulindac arm or AI only arm. All the consented participants in AI Sulindac arm will be given the study intervention.

## **18 STUDY PLAN AND SCHEDULE OF EVENTS**

The proposed study will be a non-randomized trial of postmenopausal women currently receiving aromatase inhibitor therapy for early stage hormone receptor positive breast cancer as part of their standard of care. Women will receive sulindac 150mg po BID. An additional observation group of approximately 75 women will NOT receive sulindac. We will attempt to recruit all eligible patients from the breast cancer clinics of the University of Arizona Cancer Center and Stony Brook Cancer Center.

For the observational group, approximately 75 participants will be enrolled with 60 expected to complete all measures. As all participants will have been adherent to AI therapy for a minimum of 3 months, we expect that no less than 80% will complete the study requirements, for a total of 60 fully evaluable participants.

For the sulindac treated group, approximately 100 participants will be recruited. As all participants will have been adherent to AI therapy for a minimum of 3 months, we expect that approximately 90% will continue past the observation phase to intervention phase. We estimate an additional 10% drop-out rate prior to study conclusion (12 months imaging and patient reported outcome endpoints) for a total of 80 fully evaluable participants. We have focused on women with contralateral at risk breast tissue of a BIRADS density score at least 2 ( $\geq 25\%$  BD) or scattered fibroglandular densities at least heterogenous or greater (i.e. heterogenous or mostly dense) to ensure inclusion of women with a modifiable biomarker for our primary endpoint. From our preliminary data, approximately 75% of women prescribed aromatase inhibitors in our clinics would meet this eligibility requirement.

## **19 PARTICIPANT RECRUITMENT AND INFORMED CONSENT**

Investigators and staff at the University of Arizona Cancer Center and at the Stony Brook Cancer Center will be SEPARATELY responsible for identifying and recruiting candidate participants, evaluating their

suitability for participation in the study, following participants during the treatment phase of the trial, monitoring participants for possible toxicity, and continuing to follow participants for subsequent toxicity during the post-treatment follow-up period.

Recruitment will proceed under the auspices of each center's individual Clinical Trials Office. Working in accordance with HIPAA regulations, study coordinators or treating medical staff will identify potential participants and they will be screened for eligibility by the research nurse assigned to the study. Recruitment will occur in the breast cancer and high risk clinics of the University of Arizona Cancer Center and Stony Brook Cancer Center. Currently, approximately 500 new patients with breast cancer are treated in the breast clinics of the University of Arizona Cancer Center and 400 in the Stony Brook Cancer Center annually. Thus, it can be anticipated that at least 50 patients per year would qualify for the study to meet accrual goals.

A preliminary determination of eligibility will be made through review of medical records and contact with the participating physicians.

The investigator and/or research nurse will explain all aspects of the study in lay language to the potential eligible participants, answer all questions regarding the study, and confirm eligibility. If the participant decides to participate in the study, she will be asked to review, sign and date the Informed Consent Form (ICF). The ICF has to be completed prior to initiating any study related procedures. The study agent will not be released to a participant who has not signed the ICF. Participants may terminate or withdraw from the study at any time and for any reason, including development of an AE or SAE, noncompliance, medical contraindication, or desire without prejudice.

## **20 SCREENING AND BASELINE VISIT PROCEDURES**

Only participants in the sulindac treated group will be asked to provide an optional core biopsy sample at their baseline visit; we estimate that ~75% will agree to the first. For participants who consent to breast biopsy at baseline, the breast specialist (radiologist or surgeon), as a fee for service, will use mammography images to identify two areas of increased radiographic density, located at least 2 cm apart, in the upper, outer quadrant of the contralateral (uninvolved) breast. Mammographically dense areas will be co-localized with ultrasound guidance, with their relative positions recorded by clock-face and linear distance away from the nipple. Under ultrasound guidance, a 14-gauge cutting needle will be used to obtain up to 8 tissue cores from one of the two identified high-density areas. Since 5-10 tissue cores are typically obtained during clinically indicated biopsy procedures, our tissue sampling

protocol should not impose undue participant burden or risk. Representative FFPE (formalin fixed and paraffin embedded) specimens will be reviewed at each of the two study sites separately. At Stony Brook, tissue histology will be reviewed by pathology under the direction of [name], a board-certified anatomical pathologist who specializes in breast pathology. Additional cores will be coded for processing by [name] laboratory (relocated to Cedars Sinai Medical Center January 2021) for evaluation of apoptotic, proliferation, and alternative biomarkers. At this time (January 2021), all tissues samples have been collected, processed and stored as specified in the protocol. These samples will be relocated to the Cancer Center Tissue Biobank until approved for sharing with the [name] laboratory at Cedars Sinai Medical Center under a Material Transfer Agreement. Only sample needed to complete agreed biomarker studies will be shared and all residual material returned to long term storage at either UACC or Stony Brook University. All biomarker studies after January 2021 will be conducted according to a Material Transfer Agreement between Stony Brook University and Cedars Sinai Medical Center. All pathology reviewed materials will be stored as digitized images using the Aperio Instrumentation for cross-site pathology review at Stony Brook University.

All screening and pre-washout evaluations will be completed within 21 days of initiating the study Week 1 Day 1 of the study schedule. As the target population will be postmenopausal, no serum pregnancy test will be performed.

The following events will occur at screening/baseline visits for participants in the sulindac treated group.

- a. Medical history including demographics (race, ethnicity, age, and etc.);
- b. Review medication use within the past 30 days;
- c. Review concomitant medication and supplement use;
- d. Vital signs (Blood pressure, pulse);
- e. Height and weight;
- f. Hematology (CBC/differential and platelet count);
- g. Chemistry panel (to include Urea Nitrogen, Creatinine, ALT, AST)
- h. Urinalysis
- i. Fecal occult blood test
- j. Participants will undergo a 30 day NSAID washout period.
- k. Participant may be reevaluated for study participation after the washout period.
- l. Screening/baseline lab work will be collected after the washout period.
- m. FWR-MRI and DW-MRI of contralateral, unaffected breast, quality of life questionnaire (FACT-G) and pain measurements using BPI-SF and WOMAC instruments. Participant will be given a

validated, semiautomatic electronic home blood pressure monitoring device to measure their blood pressure in each morning and evening for 3 days every 2 weeks for the first 6 weeks right after the washout period.

The following events will occur at screening/baseline visits for participants in the control arm.

- a. Medical history including demographics (race, ethnicity, age, and etc.);
- b. Review medication use within the past 30 days;
- c. Review concomitant medication and supplement use;
- d. Vital signs (blood pressure, pulse);
- e. Height and weight;
- f. Blood and urine samples obtained for research biomarkers.
- g. FWR-MRI and DW-MRI of contralateral, unaffected breast, quality of life questionnaire (FACT-G) and pain measurements using BPI-SF and WOMAC instruments

## **21 TREATMENT PLAN AND EVENTS**

### **21.1 Sulindac treated group**

Clinic visits will be scheduled at 3-month intervals ( $\pm 28$  days), during which a focused physical exam, FACT-G, pain measurements (BPI-SF and WOMAC), and indicated laboratory tests (CBC, chemistry panel) will be performed. At each visit, unused study agents will be collected, counted, and returned for appropriate disposal.

The following on study events will occur.

- a. Participants will receive and complete study log (calendar)
- b. Participants will be given a validated, semiautomatic electronic home blood pressure monitoring device to measure their blood pressure in each morning and evening for 3 days every 2 weeks for the first 6 weeks on agent and in last 6 weeks of therapy.
- c. Sulindac 150mg b.i.d. will be self-administered, by mouth, daily for a total of 12 months
- d. A chemistry panel (to include Urea Nitrogen, Creatinine, ALT, and AST) and hematology (CBC/differential and platelet count) will be performed at the post-washout, post-observation, 6 months and 12 months on sulindac visits.
- e. Blood for serum sulindac and metabolites levels will be obtained at baseline (both post-washout and post-observation visits) and at months 3, 6, 9 and 12 on sulindac.
- f. Blood pressure will be measured in the clinic at all clinic visits.
- g. Blood pressure will be monitored at home.

- h. The FACT-G, BPI-SF and WOMAC instruments will be administered at 3, 6, 9 and 12 months' clinic visit.
- i. A breast core biopsy at baseline 2 and 6 months on sulindac for planned biomarker studies and storage for future studies.
- j. Non Contrast breast MRI will be obtained at baseline, post observation and months 6 and 12 on sulindac.
- k. Unused tablets and/or empty sulindac will be returned at study visits for pill count.
- l. A urine sample for research biomarker studies will be obtained at baseline (post-washout and post-observation visits) and at 3, 6, 9, and 12 months on sulindac.
- m. A +/- 28 days window will be allowed for specimen collection and all procedures.

## **21.2 Observation group**

Clinic visits will be scheduled at 6-month intervals ( $\pm 28$  days), during which FACT-G, pain measurements (BPI-SF and WOMAC), and correlative blood and urine samples will be collected.

The following on study events will occur.

- a. The FACT-G, BPI-SF and WOMAC instruments will be administered.
- b. Non Contrast breast MRI will be obtained.
- c. A urine and blood samples collected for research biomarkers.

## **22 DEFINITIONS**

### **22.1 Follow-up**

All participants in the sulindac treated group will have a follow-up visit or telephone contact scheduled one month after the last dose of study medication/end-of-treatment to follow-up for AEs and SAEs that may have occurred during or after discontinuation from the study. AEs and SAEs that are still ongoing at the time of discontinuation will continue to be followed weekly until resolution or stabilization of condition. Abnormal laboratory values will be followed every 14 days until resolution or one month post last dose of study drug(s) whichever occurs first.

### **22.2 End of Treatment**

Study drug discontinuation is the time when study agent(s) administration is permanently discontinued for any reason.

### **22.3 Withdrawal of Participant from Study**

Participants will be withdrawn from the study under the following circumstances:

- a. Study closure,
- b. Unacceptable adverse event(s), as judged by the study physician,
- c. Participant decision to withdraw from the study or, in the judgment of the investigator, further participation would not be in the best interest of the participant,
- d. The participant is noncompliant with study procedures

## **22.4 Post-Intervention Evaluation and off-study monitoring**

A Post-Intervention office visit will be scheduled at the end of 12 months on sulindac ( $\pm 28$  days) or at early termination, if applicable, during which a focused physical exam and indicated laboratory testing (CBC, chemistry panel) will be performed. Unused study agents will be collected, counted, and returned for appropriate disposal. After completing the Post-Intervention Evaluation, study personnel will place a telephone call one month after end of the treatment to record any previously unrecorded AEs and/or review unresolved AEs. Participants will be followed until all AEs are resolved.

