- j. Study agent will be discontinued if the same event which caused suspension of the study agent occurs more than twice during the study.
- k. Participants that miss  $>28$  days of study agent during the study agent administration period, regardless of cause, will discontinue study agent and proceed with end of treatment procedures.
- l. Participants experiencing a  $\geq$  grade 2 toxicity possibly, probably, or definitely related to study agent will reduce dose by 50% if symptoms resolve within 7 days. If the symptoms recur on lower dose, the subject will be withdrawn from study and proceed with end of treatment procedures.
- m. Only one dose modification will occur in this study.

For the observational group, there is no toxicity or risk associated with this study. Thus participants will not be followed past conclusion of the study. No toxicity data will be collected and no adverse events are to be expected.

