## 25 END OF TREATMENT PROCEDURES

- a. Vital signs (Blood pressure, pulse);
- b. Hematology (CBC/differential and platelet count);
- c. Chemistry panel (to include Urea Nitrogen, Creatinine, ALT, AST)
- d. Urinalysis
- e. Review concomitant medications;
- f. Review adverse events [apply only to AI Sulindac arm];
- g. Return unused tablets/empty sulindac bottle [apply only to AI Sulindac arm];

End of Treatment procedures will be performed within 28 days of the study agent(s) administration period. For participants who are withdrawn from the study during off study agent(s) period, end of treatment procedures will be performed within 7 days of the date of withdrawal.

[figure not shown]
Following discontinuation of study agent participants experiencing adverse events will be contacted weekly by telephone or clinic visit until resolution or stabilization of condition. Abnormal laboratory values will be followed every 14 days until resolution or one month post last dose of study agent(s) whichever occurs first.

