### **27.3 Conduct of and Justification for Planned Futility Analysis**

As discussed in the funded grant submission, we would like to limit women's exposure to agents that are unlikely to effect change in the breast in a clinically meaningful way. Therefore, we will include a futility analysis for the primary trial endpoint of FWR log(Fra50) after 40 women have reached the 15-month endpoint. This analysis is for futility only, so it will not affect the overall  $\alpha$  level. Briefly, the observed results from these women will be used to compute the difference between the slope during sulindac treatment versus the baseline period. Predicted results for future participants will be generated from a log-normal distribution with the observed mean and SD. One thousand bootstrap samples with a sample size of 80 women will be generated to estimate conditional power. The study will continue if conditional power  $\geq 80\%$  is met. If we fail to pass futility, we plan to **stop accrual to the study and suspend study agent for women who are active**. We plan to follow all women who initiated trial agent to their next imaging endpoint (9 or 15 months, whichever comes first). Considering a dropout rate of 10% by 9 months and 20% by 15 months, and a planned accrual rate of 5 participants/month starting in month 6 of funding, we expect to have 40 evaluable participants followed to 15 months by approximately 3 years; by then, ~90 participants will have completed 9-month measures, and ~100 will have initiated the trial.

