In consultation with NCI, concern was raised that prior studies of AIs showing no effects of AIs on BD were based on mammography and not the more sensitive MRI method under investigation. As such, an observational (non-randomized) control group comprised of BC patients stable on an AI was included specifically to monitor for AI effect on BD using the MRD method.

Initially, the target sample size was reduced to 75 and 60 in the intervention and observation groups, respectively. A previously planned futility analysis of SUL effect on MRD after 40 participants completed 12 months of intervention was changed to the primary analysis on limited resources and slow accrual. Patients consented to banking tissue biopsies for future biomarker studies.

Modified Study Hypotheses: Because of the modification to the study design, the study hypotheses were modified as follows:

Primary

SUL 150 mg BID for 12 months will decrease MRD in postmenopausal women taking aromatase inhibitor therapy.

- a. As a sensitivity analysis of this primary hypothesis, per-study analysis described below will also be performed using only subjects who are adherent with study protocols (adherence is defined as having taken at least 80% of study agent).
- b. As a sensitivity analysis of this primary hypothesis, per-study analysis for primary hypothesis will also be performed using only those subjects with baseline BD $\geq 15\%$.

Secondary

SUL 150 mg BID for 12 months will be well tolerated and grade 3 adverse events will not exceed 10% and patients who drop out secondary to adverse events will not exceed 10%. *With low sample size of 40, only when there are no grade 3 AE or drop out secondary to AEs, can say it will not exceed 10% (point estimate is 0% with 95% Blyth-Casella-Still CI (0-7.78%).*

Reportable Outcomes

1. Change in BD from baseline at 6 and 12 months by MRD in postmenopausal women receiving AI for treatment of breast cancer and 95% confidence interval will be reported separately for:
 - a. participants in the sulindac group who started sulindac and who had at least one MRD measure on intervention,
 - b. participants enrolled and started in the observation arm with at least one MRD measure post baseline,
 - c. participants adherent to SUL intervention (same caveats as a), and

- d. in both arms but reported separately for participants with baseline BD $\geq 15\%$ (same respective caveats as a and b).

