the same subject will be selected with the Akaike Information Criterion. Log-transformed BD at each time point will be used as the outcome with adjustment for log-transformed baseline BD to improve efficiency and hence power for modeling % change in BD directly.

Note: *There is no prespecified plan to conduct a statistical test comparing change in BD between the two study groups.*

Only subjects who start SUL intervention will be included in the primary analysis. This allows us to evaluate the effect of SUL in those individuals who start intervention. 95% confidence intervals of BD change at month 6 and month 12 in the SUL group will be reported.

There are few patients whose MRD could not be obtained because of image artifact. As a sensitivity analysis, multiple imputation will be used to impute all missing MRD using patients' baseline information such as age, race, BMI, cancer stage, chemotherapy and radiation therapy information, AI use and NSAID use. Ten imputed datasets will be generated and all estimates about BD% change will be constructed using Rubin's rule. All analysis for primary hypothesis will be repeated among a subgroup of patients whose baseline BD $\geq 15\%$ and further using only SUL patients with $>80\%$ drug adherence.

For secondary hypothesis, all adverse events and severe adverse events from patients in the SUL group will be reported. The rate of patients with grade 3 or higher adverse events will be reported along with 95% Blyth-Casella-Still confidence interval.

For Reportable Outcomes

The linear mixed effect model fitted for the primary analysis will also be used to estimate the BD% changes and 95% confidence intervals at month 6 and month 12 within the observational group.

As part of this analysis for reporting purposes, we will describe the comparability of the intervention and non-random observation arm, continuous characteristics will be compared among study arms using Welch's two-sample t-test. Categorical variables will be compared using Chi-square test and exact p-values based on simulations may be reported if there is data sparsity. Any differences will be reported.

Percentage change in BD during the 3-month observation period in the SUL group will be reported with its 95% confidence interval (*i.e.* % change as $[BD \text{ at the end of observation period} - BD \text{ at the beginning of observation period}] / BD \text{ at the beginning of observation period}$).

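### No general rule keeps women who stop sulindac early on the MRI and questionnaire schedule, so month-12 results describe mainly women still on drug, not all who start

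*Protocol*

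**What the plan says.** **Protocol, what happens on stopping.**
- Section 22.4 places the closing visit at 12 months "or at early termination, if applicable, during which a focused physical exam and indicated laboratory testing (CBC, chemistry panel) will be performed". Tablets are returned, and a later telephone call covers adverse events.
- Section 25 lists vital signs, blood tests, urinalysis, medication and adverse-event review, and tablet return. Its timing rule is "End of Treatment procedures will be performed within 28 days of the study agent(s) administration period". It names no MRI, BPI-SF, WOMAC or FACT-G.
- Section 24 routes stoppers to that list: item h (event unresolved at the lower dose), item l (recurrence at the lower dose) and item k, under which women who miss more than 28 days, "regardless of cause, will discontinue study agent and proceed with end of treatment procedures".
- Section 21.1 sets the imaging schedule: "Non Contrast breast MRI will be obtained at baseline, post observation and months 6 and 12 on sulindac". Questionnaires are due at months 3, 6, 9 and 12.

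**Protocol, exceptions.**
- Section 10.6 takes women with grade 3 or higher hypertension off the intervention but follows them to study end if they agree. Section 24e removes the same women from study.
- Section 27.3, for a study-wide futility stop only: "We plan to follow all women who initiated trial agent to their next imaging endpoint".

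**SAP.**
- The primary analysis includes only women who start sulindac, and the stated reason is: "This allows us to evaluate the effect of SUL in those individuals who start intervention".
- Reportable outcome 1a covers "participants in the sulindac group who started sulindac and who had at least one MRD measure on intervention".
- A sensitivity analysis multiply imputes all missing MRI density (MRD) from baseline information. Image artifact is the only cause of missing MRD that is named.
- Pain and quality-of-life changes are reported for women who initiated sulindac, with no missing-data sensitivity analysis.

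**The concern.** Women leave treatment for reasons that may be related to the drug: toxicity, intolerance or, for pain, lack of relief. If stopping the drug also ends outcome measurement, the measured women are a selected subset of starters. The SAP's stated target (starters) and its data (mainly women still on drug) then differ, and the gap is widest at month 12, the main time point.

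The SAP itself has a secondary hypothesis about drop-out due to adverse events, so missingness linked to tolerability was foreseen. Yet no planned analysis treats stopping as a cause of missing outcomes. A reader of the final report could take the month-12 change as what to expect when a woman is started on sulindac.

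**Working it through.** **1. What an early stopper contributes if sections 21.1, 24 and 25 are followed.**
- Stops between months 3 and 6: month-3 questionnaires and adverse events, but no on-drug MRI. She falls outside reportable outcome 1a.
- Stops between months 6 and 12: a month-6 MRD, which the mixed model keeps, and questionnaires up to stopping. No month-12 MRI or questionnaire is assured.

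**2. The plan's own sample size.** Inputs from section 27.2: 80 evaluable women, 0.368 SD, two-sided alpha 0.017, 80% power. With a paired t test (noncentral t), power at n = 80 is 0.801 and the smallest n reaching 80% is 80, so the figure reproduces. It counts evaluable women after up to 20% loss from 100 and says nothing about those lost.

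**3. Share of starters without month-12 data.** Sections 8 and 18: 100 recruited, about 90% go on to sulindac, then a further 10% are lost.
- Starters: 100 × 0.9 = 90.
- Evaluable: 90 × 0.9 = 81, stated as 80.
- Missing: 10/90 = 11.1% (9/90 = 10% if 81 is used).

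The number with no on-drug MRI at all cannot be fixed. Section 27.3 plans 10% loss by study month 9, which is six months on drug. If that is the same 10% lost before sulindac starts, the number is near zero. If the loss falls after the start, it is about 10%.

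**4. Size of the possible gap.** Let d be the share of starters who stop and are unmeasured, and f the stoppers' effect as a fraction of the stayers' effect.
- All-starter effect = stayer effect × [(1 − d) + d × f].
- Overstatement by a completer estimate = 1/[(1 − d) + d × f] − 1.

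| d | f = 1 | f = 0.5 | f = 0 |
|---|---|---|---|
| 0.05 (assumption) | 0% | 2.6% | 5.3% |
| 10/90 (planning figures) | 0% | 5.9% | 12.5% |
| 0.20 (assumption) | 0% | 11.1% | 25% |

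At d = 10/90, the 0.8-unit fall in worst pain used in section 27.2 becomes 0.8 × 0.944 = 0.76 (f = 0.5) or 0.8 × 0.889 = 0.71 (f = 0) across all starters. With f = 0, 0.368 SD becomes 0.327 SD, and power with all 90 measured would be 0.75 (SD held constant).

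**5. What the planned safeguards do.** The mixed model assumes that missingness depends only on observed data: baseline density, age, BMI and any month-6 MRD. The imputation variables listed are baseline ones, and stopping sulindac is not among them. Both therefore fill in a stopper as if she resembled measured women with similar observed data. The adherence analysis restricts to women who took about 80% or more of the drug, which moves further from starters.

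**The case against.** The case against has several sound parts.

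- **The lists are not exhaustive.** Section 22.4 describes one visit for completers and early stoppers alike, and completers get their MRI and questionnaires from section 21.1. A reader might infer that the protocol forbids imaging after stopping. It does not; it is silent. What stands is that section 21.1 counts months on sulindac, which an early stopper does not reach, and no other text brings her back.
- **Stoppers do not vanish.** A reader might infer that a woman who stops before month 6 contributes nothing. Month-3 pain and FACT-G data and her adverse events remain, and later stoppers give a month-6 MRD. Women on a reduced dose or a permitted drug holiday also stay in the study.
- **Missing MRD is not ignored.** The SAP imputes all of it. That stands, with the limits shown in the working.
- **The arithmetic is not the SAP's estimator.** It describes a completer mean, treats every planned loss as a stopper, and depends on f. The protocol gives no reasons for drop-out, and women who withdraw consent would be missing under any rule. The SAP also made the analysis after 40 completers primary, so the actual share may differ.
- **Direction for density.** No passage links stopping to a woman's density change.
- **On-drug activity is a legitimate target** for a single-arm feasibility study, and outcome 1a states its population openly. That is a reason to label the result accordingly, not to describe it as the effect in starters.

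**Conclusion.** The point holds in limited form. No general rule keeps early stoppers on the MRI and questionnaire schedule. The one exception for individual stoppers, in section 10.6, conflicts with section 24e, and those passages must be reconciled. Month-12 results, and month-6 MRD for earlier stoppers, therefore rest mainly on women still on drug, while the SAP describes the effect in those who start. Nothing planned addresses missingness caused by stopping, and pain and quality of life have no missing-data sensitivity analysis at all.

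On planning figures the possible overstatement at month 12 runs from 0% to 12.5%, with about 6% at half effect. This assumes that all 10 missing starters are stoppers and that a completer estimate is used. A reader might go further and conclude that the density result is biased towards benefit, or that the error is 25% or more. The documents support neither: the first needs stoppers to have a smaller density effect, and the second needs a stopping share of at least 20%, which the documents do not give.

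**What to change.** Section 4.4 says participation has concluded, so scans cannot be added. Amend the SAP instead:
1. Describe the month-6 and month-12 results as effects mainly in women still on drug, and drop or qualify the claim about those who start.
2. Tabulate starters without month-6 and month-12 MRD and pain data, by reason (adverse event, missed drug, withdrawal of consent, artifact, other).
3. Add a sensitivity analysis for MRD and pain that gives stoppers no drug effect. One choice is the observation-arm change, used as an imputation value and not as a between-group test. That respects section 4.2, section 27.2 and the SAP, which rule out using that arm for a statistical comparison. Because eligibility differs between arms (section 15), state this as an assumption.
4. Reconcile sections 10.6 and 24e on follow-up after grade 3 or higher hypertension, and report what was done.

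Had the trial still been running, the protocol should also have separated off drug from off study and kept the month-6 and month-12 MRI and questionnaires for consenting women who stop.

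Cost: one extra analysis and one table. The starter estimate may be less favourable than the on-drug one.
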